To minimize the risk of severe adverse event in frail subjects enrollment of Elderlies-cohort will start after that 4-week safety results in Adults-Cohort will be available. Moreover, as it is a first in human trial, we have scheduled volunteers to be enrolled according to a strict frame of authorization rules. In particular, each arm includes two groups (A and B). Group As are made of 3 volunteers each to be enrolled throughout a week. The occurrence of SAE within 48h since the injection will be reported to data safety monitoring board (DSMB) and the enrolment suspended until a direct effect of the vaccination is excluded. Group Bs are made of 12 participant each to be enrolled over a week. DSMB provide binding advice on sequential enrollment across groups and arms; this is:

- enrolment of Arm-1 group B and Arm-2 group A is bound to a positive decision on 7-day safety of Arm-1 group A;
- enrolment of Arm-2 group B and Arm-3 group-A is bound to a positive decision on 7-day safety of Arm-2 group A;
- enrolment of Arm-3 group B is bound to a positive decision on 7-day safety of Arm-3 group A;
- enrolment of Arm-4 group A is bound to a positive decision on 4-week safety Arm-1;
- enrolment of Arm-4 group B and Arm-5 group A is bound to a positive decision on 7-day safety of Arm-4 group A;
- enrolment of Arm-5 group B and Arm-6 group-A is bound to a positive decision on 7-day safety of Arm-5 group A;
- enrolment of Arm-6 group B is bound to a positive decision on 7-day safety of Arm-5 group A.

Figure 8 reports the flow-charts for authorization and enrollment.

[figure not shown]

Figure 8 Study design and enrollment flow charts according to DSMB binding decisions

6. Recruitment and withdrawal

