7.7. Vaccination sequence

For safety reasons enrolment of *first in human* vaccine administration will be carried out on a weekly sequence in the six different arms. Each arm will be divided into 2 groups. Group-A are made of 3 volunteers each and group-Bs are made of 12 volunteers each.

At the beginning of the study clinical center will smoothly screen eligible subjects.

At enrollment on day 1 the first participant (arm 1 group-A) will be vaccinated ahead of any other participants and the profile of adverse events will be reviewed 48 hours after vaccination. Provided there are no safety concerns, as assessed by the local medical investigators, another two participants will be vaccinated at the same dose after at least 48 hours has elapsed following the first participant. Thus within one week, three participants will be vaccinated.

The following week the three participants vaccinated will undergo clinical screening for AE including a medical visit and a laboratory tests up to 7 days after vaccination. DSMB will analyze data on safety for arm 1 group-A and provide binding advice for the eventual enrolment. Eventual enrollment will include two blocks of participants this is:

- A. Arm 1 group-B (12 participants)
- B. Arm 2 group-A (3 participants)

Participants in arm 2 group-A will be scheduled for vaccination similarly to those vaccinated in arm 1 group-A, 48 hours apart from each other, provided there are no safety concerns, as assessed by the local medical investigators. Participants in arm 1 group-B will be smoothly vaccinated throughout the week.

The participants vaccinated in arm 2 group-A and arm-1 group-B undergo clinical screening for AE including a medical visit and a laboratory tests up to 7 days after vaccination. DSMB will analyze data on safety for arm 2 group-A and provide binding advice for the eventual enrolment. Eventual enrollment will include two blocks of participants this is:

- A. Arm 2 group-B (12 participants)
- B. Arm 3 group-A (3 participants)

Participants in arm 3 group-As will be scheduled for vaccination similarly to those vaccinated other group-As, 48 hours apart from each other, provided there are no safety concerns, as assessed by the local medical investigators. Participants in arm 2 group-B will be smoothly vaccinated throughout a week.

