9.1. Definitions

Adverse event (AE). (AE) is any untoward medical occurrence in a participant, which may occur during or after administration of the vaccine and does not necessarily have a causal relationship with the intervention. An AE can therefore be any unfavorable and unintended sign (including an abnormal laboratory finding), symptom or disease temporally associated with the study intervention, whether or not considered related to the study intervention.

Adverse reaction (AR). An AR is any untoward or unintended response to the vaccine. This means that a causal relationship between the vaccine and an AE is at least a reasonable possibility, i.e., the relationship cannot be ruled out. All cases judged by the reporting medical Investigator as having a reasonable suspected causal relationship to the vaccine (i.e. possibly, probably or definitely related to the vaccine) will qualify as adverse reactions.

Unexpected adverse reaction (UAR). An UAR is any untoward or unintended response to the vaccine, the nature and severity of which is not consistent with the information about the medicinal product in question set out in the investigator brochure (IB) or summary of product characteristics.

Serious adverse event (SAE). A SAE is an AE that results in any of the following outcomes, whether or not considered related to the study intervention.

- A. Death
- B. Life-threatening event (i.e., the participant was, in the view of the Investigator, at immediate risk of death from the event that occurred).
- C. Persistent or significant disability or incapacity (i.e., substantial disruption of one's ability to carry out normal life functions).
- D. Hospitalization, regardless of length of stay, even if it is a precautionary measure for continued observation.
- E. Significant medical intervention including surgery or administration of drugs (examples of such medical events include allergic reaction requiring intensive treatment in an emergency room or clinic, blood dyscrasias, or convulsions regardless eventual need of hospitalization)
- F. A grade ≥ 3 abnormalities on safety blood test according to Common Terminology Criteria for Adverse Events (CTCAE v.4 and MedDRA 12.1).

Serious adverse reaction (SAR). A SAE (expected or unexpected) that, is in the opinion of the reporting Investigator, believed to be possibly, probably or definitely due to the vaccine.

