9.8. Halting rules and study termination due to safety issue

Safety halting rules have been developed considering the fact that this is a *first-in-human* dose escalation study. Solicited adverse events are those listed as in section 9.2, occurring within the first 7 days after vaccination (day of vaccination and six subsequent days). Unsolicited adverse events are AE other than the solicited AEs occurring within the first 7 days, or any AEs occurring after the first 7 days after vaccination.

Enrolment of participants in one arm will be upheld if:

- A. Solicited local adverse events (site of injection): 2 or more vaccinations in a group are followed by the same severe solicited local adverse event beginning within 2 days after vaccination (day of

vaccination and one subsequent day) and persisting at severe for >48 hrs and these are deemed possibly, probably or definitely related to study interventions.

- B. Solicited systemic adverse events: If 2 or more vaccinations in a group are followed by the same severe solicited systemic adverse event beginning within 2 days after vaccination (day of vaccination and one subsequent day) and these are deemed possibly, probably or definitely related to study interventions.
- C. Unsolicited adverse events: If 2 or more vaccinations in a group are followed by the same serious unsolicited adverse event (including the same laboratory adverse event) and relation with vaccination cannot be immediately excluded.
- D. One participant with serious adverse event considered possibly, probably or definitely related to vaccination occurs
- E. Life-threatening condition when relation with study intervention cannot be immediately excluded.
- F. Death when relation with study intervention cannot be immediately excluded.

If a halting rule has been met, we will inform the regulatory authority. Moreover, before restarting enrollment the DSMB should exclude that AE has no immediate causal relation with the vaccine or that benefit of vaccination outweigh risk of further AE occurrence. In these latter case Ethical committee should be involved in the decision. Halting rules apply to one dose and the next higher one, so that if halting rule is met for the highest dose, only this arm is upheld. If halting is met for intermediate dose, two arms are held. If halting rule is met for the lowest dose all the study is stopped pending on the investigation of causal association between AE and vaccination (DSMB advice).

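### Halting rules A to C count repeat events by *group*, a word the protocol also uses for parts A and B of an arm; read literally, one severe non-serious reaction in each part meets no rule

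*Protocol*

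**What the plan says.** Section 9.8 opens with "Enrolment of participants in one arm will be upheld if" (from the context, *upheld* means put on hold) and lists six triggers.

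- Rule A: "2 or more vaccinations in a group are followed by the same severe solicited local adverse event". Onset must fall on the day of vaccination or the day after, the event must stay severe for more than 48 hours, and it must be at least possibly related.
- Rule B uses the same count for solicited systemic events, without the persistence condition.
- Rule C uses the same count for serious unsolicited events.
- Rule D needs one case: "One participant with serious adverse event considered possibly, probably or definitely related to vaccination occurs". Rules E and F cover life-threatening events and deaths.

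The section then gives the scope: "Halting rules apply to one dose and the next higher one". It spells this out by dose. A rule met at the highest dose holds that arm only, at the intermediate dose two arms, and at the lowest dose the whole study.

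Section 5 says "each arm includes two groups (A and B). Group As are made of 3 volunteers each to be enrolled throughout a week", and section 7.7 says "Group-A are made of 3 volunteers each and group-Bs are made of 12 volunteers each". Group B opens only after a binding positive DSMB decision on the 7-day data of group A. It is then dosed within about a week; for Arm 1, "Participants in arm 1 group-B will be smoothly vaccinated throughout the week".

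Elsewhere *group* means arm: protocol section 10.2 compares groups in that sense, and SAP Table 1 labels the six arms as treatment groups. SAP section 4.11.7 leaves DSMB procedures to the charter.

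**The concern.** The section that stops a first-in-human trial counts events in one unit and holds enrolment in another, and nothing links the two. If *group* means A or B, a reaction in A does not carry over to B: two cases among the 12 in B meet the rule, but one in A plus one in B, also two of 15 at the same dose, do not.

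What is at stake is whether that split pair is a mandatory hold or a matter of judgement. The difference is largest at the lowest dose, where a met rule stops the whole study. The escalation gates do not close the gap. Within each cohort, the next steps rest on the 7-day data of a group A; only the gate from Arm 1 to Arm 4 uses a whole arm. A second case in group B therefore forces a stop only through 9.8.

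**Working it through.** **Step 1. Structure.** Six arms of 3 + 12 give 6 × 15 = 90, the planned total. The documents state no operating characteristics for the halting rules, so there is no further figure to reproduce.

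**Step 2. One case, two readings.** Take the same severe, non-serious, expected, related solicited reaction once in A and once in B of one arm, with the onset (and for rule A the persistence) conditions met.

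| Rule | *Group* = A or B | *Group* = arm |
|---|---|---|
| A (local) or B (systemic) | 1 and 1: not met | 2 of 15: met |
| C | not met (solicited, not serious) | not met |
| D, E, F | not met (not serious) | not met |

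**Step 3. Which events are left.**
- Serious related events meet rule D at one case, so rule C is almost unaffected by its counting unit.
- Section 9.5 suspends enrolment for a SAR or SUSAR within week 10 of the study. Section 9.1 words a SUSAR as a severe (not serious) reaction inconsistent with the investigator brochure, so an unexpected severe reaction may be caught at one case. Hence the restriction to expected reactions.
- Under the 9.2 scale, severe implies invasive intervention or hospital care. Section 9.1 counts as serious "Hospitalization, regardless of length of stay, even if it is a precautionary measure for continued observation", so such reactions largely fall under rule D.
- Section 9.6 points instead to Table 1. Of the 13 solicited terms in 9.2, Table 1 has rows for three: fever (severe above 39.0), erythema (above 100 mm) and swelling (above 50 mm). These are the practical residual.

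**Step 4. Size.** Let p be the true rate of one qualifying event type, and q the chance that the DSMB opens B after 1 of 3 in A. Events are taken as independent. The readings differ only when exactly one event falls in A and exactly one in B:

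loss = 3p(1−p)² × q × 12p(1−p)¹¹ = q × 36p²(1−p)¹³.

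The maximum is where 2/p = 13/(1−p), that is p = 2/15 = 13.3%. As a check at q = 1, the loss equals P(at least 2 of 15) minus [1 − P(at most 1 of 3) × P(at most 1 of 12)].

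| p | Rule met, arm count (%) | Rule met, A/B count (%) | Loss, q = 1 (points) | Loss, q = 0.5 (points) |
|---|---|---|---|---|
| 1% | 0.96 | 0.65 | 0.3 | 0.2 |
| 2% | 3.53 | 2.43 | 1.1 | 0.6 |
| 5% | 17.10 | 12.48 | 4.6 | 2.3 |
| 10% | 45.10 | 35.94 | 9.2 | 4.6 |
| 13.3% | 61.34 | 51.38 | 10.0 | 5.0 |
| 20% | 83.29 | 75.37 | 7.9 | 4.0 |

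The two middle columns assume all 15 are dosed (q = 1). At q = 0 the loss is zero.

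**Step 5. After one event in A, with B opened.** The arm count needs at least 1 of 12 in B; the literal count needs at least 2 of 12. The chances are 11.4% against 0.6% (p = 1%), 21.5% against 2.3% (2%), 46.0% against 11.8% (5%) and 71.8% against 34.1% (10%). The starting point is itself uncommon at low rates: P(exactly 1 of 3) is 2.9%, 5.8%, 13.5% and 24.3%.

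**Step 6. Doses at stake in the same arm.** Assume 12 doses spread evenly over 5 or 6 days, with the group B event on a random dosing day. On average 4.8 or 5.0 doses remain at a lag of 0 days, 2.9 or 3.3 at 1 day, 1.4 or 2.0 at 2 days, and 0.5 or 1.0 at 3 days. Rule B acts at about 0–1 day and rule A at about 2–3 days. This leaves out doses in higher-dose arms that a hold would also stop.

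**The case against.** The strongest case is that 9.8, read as a whole, already means arm. Its stem holds an arm, and its scope text speaks of a rule being met for a dose, which is most naturally counted per dose. Sections 5 and 7.7 attach a letter when they mean A or B; 9.8 does not. On that reading nothing is lost, and the charter may say so outright. This stands as the likelier intent, but it remains an inference.

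Next, the gap needs a second contested reading, that Table 1 and not 9.2 decides what is severe. Section 9.8 itself refers to 9.2 for solicited events. Fever is narrower still: section 7.8 manages any fever from 37.5 °C as suspected COVID-19 and allows admission for observation, and admission would make a related fever serious. This also stands, and it limits the residual to three measured signs. On the other side, if severe always meant serious, rules A and B would rarely act before rule D.

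Third, written safeguards exist. The local investigator may place the study on hold (9.7). The principal investigator may take situations short of a halting rule to the DSMB, which meets weekly during enrolment and can withhold it (13.1). They are real, but discretionary.

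A reader might infer that two severe reactions could pass unseen, or that serious events escape. The documents do not support either. The DSMB has reviewed the first event before B opens, and one related serious event meets rule D.

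**Conclusion.** The wording is ambiguous on a safety trigger, and the documents do not settle it. The point holds in a narrow form: on the literal reading, a split pair of severe, non-serious, expected solicited reactions in one arm meets no halting rule, and in practice these are fever, erythema or swelling graded by Table 1. On the arm reading the same pair is a mandatory hold.

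The loss figures are upper bounds for one event type in one arm. They assume independent events, onset, relatedness and (for rule A) persistence conditions met, and a DSMB that always opens B. The 10.0-point figure should not be read as an expected loss: it needs a rate of 13.3% as well. Event rates are assumed throughout. If *group* means arm, the loss is zero.

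This is a cheap improvement of minor severity, not evidence that the plan leaves participants without protection.

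**What to change.** In rules A, B and C of section 9.8, replace *in a group* with *in an arm (groups A and B combined, counted cumulatively)*. Check the DSMB charter and align it if it uses another unit. The new wording agrees with the stem and scope text of 9.8.

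No extra data, participants or outputs are needed: DSMB outputs follow the SAP, and SAP Table 2 already groups adverse events by arm.

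The cost is a slightly higher chance of a hold, by at most the loss shown above. A hold is not trivial. It brings notice to the regulatory authority and DSMB review before restart, and the ethics committee is involved if restart rests on benefit outweighing risk. At the lowest dose the whole study waits.

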10.1. Sample size

This is a descriptive phase I first in human trial to assess safety and immunogenicity of three different vaccine doses. Overall, the trial will include 90 participants and no formal sample size calculation is carried out.

10.2. Statistics analysis

This is a descriptive safety study, where participants will be vaccinated with different doses of GRAd-COV2 against SARS-CoV-2. Forty-five participants per age cohort (for a total of 90 subjects) will be vaccinated in total. This sample size should allow an estimation to be made of the frequency and magnitude of outcome measures, rather than aiming to obtain formal statistical significance for differences between groups.

Safety data will be presented according to frequency, severity and duration of adverse events. The primary analysis for immunogenicity will be to assess the difference in magnitude of SARS-CoV-2 specific T-cell and antibody responses between the groups. We will assess vaccine immunogenicity by comparing the change in these immunological parameters from baseline to different endpoints. At the end of the study, we expect to

6 measures per participant for T-cell response and antibody level. We will explore the possibility to describe kinetics of these parameters through non-parametric test for comparison of:

- A. *within-the-arm medians* at different times (i.e. baseline vs. either week-2, week-4, week-8, week-12 and week 24) between groups at different follow-up time);
- B. *within the Adults-Cohort medians* at specific time (i.e. Arm-1 vs. either Arm-2 or Arm-3 at baseline, week-2, week-4, week-8, week-12 or week-24).
- C. *within the Elderlies-Cohort medians* at specific time (i.e. Arm-4 vs. either Arm-5 or Arm-6 at baseline, week-2, week-4, week-8, week-12 or week-24).
- D. *Across the cohort medians at specific time* (i.e. Arm-1 vs. Arm-4; Arm-2 vs Arm-5; Arm-3 vs. Arm-6 at baseline, week-2, week-4, week-8, week-12 or week-24)

Explorative kinetics model based on regression techniques for correlated measures will be carried out if normal distribution of data is proven.

11. Data Management

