4.2.5. Deliverables

- 1. Within five months after the study approval a report on safety and immunogenicity at 4 weeks for Adult-Cohort will be developed; this report will include:
 - a. an analysis of safety issue in the three adults-arms
 - b. pivotal consideration used for authorizing enrollment in the Elderlies-Cohort
 - c. a preliminary analysis of immunogenicity in the three adults-arms aimed at identifying the most convenient doses to be used in the eventual phase 2/3 trial.
- 2. Within seven months after the study approval a report on safety and immunogenicity at 4 weeks for Elderly-Cohort will be developed; this report will include pivotal consideration on
 - a. an analysis of safety issue in the three elderlies-arms
 - b. a preliminary analysis of immunogenicity in the three elderlies-arms aimed at identifying the most convenient doses to be used in the eventual phase 2/3 trial.
 - c. comparison of safety and immunogenicity between adults and elderlies (across the cohort comparison) to define the most convenient doses to be used either in general population or special groups at risk.
- 3. Within one year since study approval final report will be produced including:
 - a. Final analysis on safety and immunogenicity at 24 weeks after vaccination in Adults-Cohort
 - b. Final analysis on safety and immunogenicity at 24 weeks after vaccination in Elderlies-Cohort

[figure not shown]

Figure 6 Estimated time (week) for enrollment and follow-up for Adults-Cohort. Figures within cells represent time (in weeks) after vaccination. Grey bars represent timing of authorization for enrollment. Blue cells represent time of participants' enrollment. Emerald green cells represent time for safety assessment. Golden cells represent time of sampling carried out for immunogenicity assay on frozen specimens. Red cells represent time of sampling carried out for immunogenicity assay on fresh samples. Orange cells represent milestones (letters represent the specific milestone). Olive green cells represent deliverables (numbers represent the specific deliverable).

[figure not shown]

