## 1 INTRODUCTION

The analyses described in this SAP are based upon the following study documents:

- Study Protocol, Version 2.0 (September 8, 2020)
- electronic Case Report Form (eCRF), Version 4 (generated on August 4, 2020)
- DSMB Charter, Version 2.0

Per protocol, the collected data will be analyzed and reported in three steps according to stages achieved during the course of the study, ie:

Delivery 1: Interim Analysis 1

A report on safety and immunogenicity at 4 weeks for Adults-Cohort will be developed; this report will include:

- a. an analysis of safety issue in the three adults-arms;
- b. pivotal considerations for authorizing enrollment in the Elderlies-Cohort;
- c. a preliminary analysis of immunogenicity in the three adults-arms aimed at identifying the most convenient dose to be used in the eventual phase 2/3 trial.

Delivery 2: Interim Analysis 2

A report on safety and immunogenicity at 4 weeks for Elderlies-Cohort will be developed; this report will include pivotal considerations on:

- a. an analysis of safety issues in the three elderlies-arms
- b. a preliminary analysis of immunogenicity in the three elderlies-arms aimed at identifying the most convenient doses to be used in the eventual phase 2/3 trial.
- c. comparison of safety and immunogenicity between adults and elderlies (across the cohort comparison) to define the most convenient dose to be used either in general population or special groups at risk.

Delivery 3: Final Analysis

Within one year since LSLV final report will be produced including:

- a. Final analysis on safety and immunogenicity at 24 weeks after vaccination in Adults-Cohort
- b. Final analysis on safety and immunogenicity at 24 weeks after vaccination in Elderlies-Cohort

Analyses described hereafter will cover all these three stages of the study with applicable closures on selected analyses if a stage requires.

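### The intermediate-versus-high dose difference is shown only arm by arm and never estimated directly with an interval, although the interim reports are meant to help identify a dose

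*Protocol*

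**What the plan says.** Protocol 10.2 lists four sets of immunogenicity comparisons. Item A compares visits within an arm. Item B covers dose within the adult cohort: "i.e. Arm-1 vs. either Arm-2 or Arm-3 at baseline, week-2, week-4, week-8, week-12 or week-24". Item C covers dose within the elderly cohort: "i.e. Arm-4 vs. either Arm-5 or Arm-6 at baseline, week-2, week-4, week-8, week-12 or week-24". Item D pairs equal doses across cohorts: "i.e. Arm-1 vs. Arm-4; Arm-2 vs Arm-5; Arm-3 vs. Arm-6 at baseline, week-2, week-4, week-8, week-12 or week-24". Arm-2 vs Arm-3 and Arm-5 vs Arm-6 appear in none of them.

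The section gives these comparisons a modest status. They are introduced with "We will explore the possibility to describe kinetics of these parameters through non-parametric test for comparison of", and the sample size is said to serve estimation "rather than aiming to obtain formal statistical significance for differences between groups". The same section also names the between-group difference in response magnitude as the primary immunogenicity analysis, without a reference arm. Protocol 4.2.3 likewise promises within-cohort comparisons across doses without naming one.

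The dose question is in Protocol 4.2.5. Deliverable 1c is "a preliminary analysis of immunogenicity in the three adults-arms aimed at identifying the most convenient doses to be used in the eventual phase 2/3 trial", and 2b is the counterpart for the elderly. SAP Section 1 repeats both.

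SAP 4.10 provides summaries by visit and arm, geometric mean titres for neutralisation, and plots for comparing arms visually. SAP Table 3 sets the arms side by side. SAP 4.13 plans no hypothesis tests. SAP 4.2 gives a decimal-place rule for confidence intervals, but SAP 4.10 specifies no interval for any difference between doses.

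**The concern.** Choosing among three doses includes choosing between the upper two. Comparisons of each with the lowest dose address whether Arm-2 differs from Arm-1 and whether Arm-3 differs from Arm-1. Neither addresses whether Arm-2 differs from Arm-3.

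If only the comparisons with the lowest dose carry a p-value, it is natural to read the pattern of significance as a ranking. That reading fails in two ways:

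- **Equal higher doses look different**, because by chance only one of them reaches significance against the lowest.
- **A real gain from intermediate to high is hidden**, because both reach significance.

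Both errors would bear on the judgement that Deliverables 1c and 2b are meant to inform.

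**Working it through.** **Figures in the plan.** The documents state no alpha, power, effect size or SD for immunogenicity, so there is no planned figure to reproduce. From the documents come 15 participants per arm, three arms per cohort, and six measures per participant (baseline and weeks 2, 4, 8, 12 and 24).

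**Coverage of the list.** Three arms give 3 × 2 / 2 = 3 dose pairs per cohort. Two are listed. Over six time points that is 2 × 6 = 12 comparisons per endpoint and cohort. The full set is 3 × 6 = 18. For both cohorts the count goes from 24 to 36.

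**What ranking by significance would do.** The assumptions are ours: normal data on the log scale, SD 1, 15 per arm, two-sided rank-sum tests at 0.05. Rates come from simulations of 5,000 to 40,000 runs per scenario; ranges show the spread between runs. True means are in SD units for Arm-1, Arm-2, Arm-3; the same holds for Arms 4 to 6.

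| True means | Exactly one listed test significant | Both listed tests significant | Direct Arm-2 vs Arm-3 significant |
|---|---|---|---|
| 0, 0.5, 0.5 | 25–26% | 11% | about 5% |
| 0, 0.8, 0.8 | 34% | 35% | about 5% |
| 0, 1, 1 | 28–29% | 58% | about 5% |
| 0, 1.5, 1.5 | 5% | 94% | about 4–5% |
| 0, 1, 2 | 28–29% | 71–72% | 71–72% |
| 0, 1.5, 2.5 | 3% | 97% | 71–72% |

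A check on the first row: each listed test is significant in about 23.4% of runs and both in 10.9%, so exactly one is significant in 2 × (23.4 − 10.9) = 25.0%.

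In the first four rows the higher doses are equal, so the second column is the rate of a false ranking. It peaks at moderate effects and falls when both doses are far above the lowest. In the last two rows the high dose is truly 1 SD better. At 0, 1, 2 the listed pair separates the higher doses in about 28–29% of trials, against about 71–72% for the direct test, a gap of roughly 43 points. At 0, 1.5, 2.5 it separates them in only 3%.

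**What a direct contrast can deliver at 15 per arm.**

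- Standard error of a difference: √(2/15) = 0.365 SD.
- 95% interval half-width: 2.048 × 0.365 = 0.75 SD.
- Difference detectable with 80% power: (1.960 + 0.842) × 0.365 = 1.02 SD. For a rank test it is 1.02 / √0.955 = 1.05 SD.
- Power at 0.5 SD: Φ(0.5/0.365 − 1.960) = 28%. At 1.0 SD it is 78%.

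The direct estimate addresses the right question but is imprecise. That favours an interval over one more p-value.

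**The case against.** The strongest reply is that the documents adopt no significance-based dose rule. A reader might infer from the list in Protocol 10.2 that the dose is to be settled by the tests against the lowest arm. The documents do not support that. The tests are offered as something to explore in describing kinetics, significance is disclaimed in the same section, SAP 4.13 plans no tests, and the deliverables do not refer to the 10.2 list. The dose is to be considered in a report that also covers safety. This stands, and it confines the error rates above to a reader who ranks doses by significance.

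A reader might also infer that the two higher doses are never compared. That is too strong as well. Protocol 4.2.3 is openly worded, and the SAP tables and plots put all three arms of a cohort next to each other, so a descriptive comparison is available. What is missing is an estimate of the difference with its uncertainty. Side-by-side medians or geometric means do not supply one, and it is what a stated aim of estimation calls for.

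The simulation also ignores values at the assay floor (anti-S concentrations below quantification set to 1.9, titres below 1:10 set to 5). Many floor values would change the rates. They would not turn two comparisons with the lowest dose into a comparison of the other two.

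Low power at 15 per arm is a fair caution. It argues for showing the interval, so that readers see how weakly the higher doses are separated.

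**Conclusion.** This is a real but limited specification gap. The within-cohort lists cover two of the three dose pairs, and the SAP estimates no between-dose difference at all, so the intermediate-versus-high difference is described but not quantified. The documents do not show that the dose decision rests on the wrong tests.

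If the pattern of significance were used as a ranking, false separation of equal higher doses would occur in about 26% to 34% of trials for effects of 0.5 to 1.0 SD, against about 5% for a direct test. With means of 0, 1 and 2 SD, a real difference would be separated in about 29% against about 71%. These figures depend on assumed effect sizes, normal log-scale data and a 0.05 level, none of which the documents give. With equal higher doses 1.5 SD above the lowest, the false-separation rate falls to about 5%. The point is best classed as a cheap improvement.

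**What to change.** 1. In Protocol 10.2 B and C and in SAP 4.10, add Arm-2 vs Arm-3 and Arm-5 vs Arm-6.
2. Report all three within-cohort dose pairs as a geometric mean ratio or a Hodges-Lehmann shift, each with a 95% confidence interval and labelled exploratory. Say which measure applies to which assay, since a geometric mean ratio depends on the imputed value where many results lie at the floor.
3. State that dose comparisons rest on these direct estimates and not on which arms differ significantly from the lowest dose.
4. Keep the baseline comparisons, or at least baseline summaries by arm. Dropping them to offset the new contrasts would be a false economy: arms are filled in sequence and no random allocation to dose is described, so baseline comparability helps in reading later differences.

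The cost is protocol and SAP wording plus one further contrast per cohort, endpoint and visit on data already collected. For the SAP it also means introducing between-arm estimates where there are none now. At the interim analyses the load is smaller still for ELISpot and neutralisation, which SAP 4.14 reports only at week 2 and week 4 respectively. The downside is a few more exploratory estimates with wide intervals: about ±0.75 SD, with 80% power only near 1 SD.
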